Clinical Laboratories:	UPMC CLSI Lab [name]	Automated Testing Laboratory Children's Hospital of Pittsburgh UPMC [name]		

Manufacturer:	Hope Pharmaceuticals.
Study Rationale:	
Cystic fibrosis (CF) is the most common severely life-shortening genetic disease of Caucasians. Tenacious mucus plugs the airways and allows for bacterial biofilms to grow. Ongoing infections lead to bronchiectasis and ultimately death from chronic respiratory failure (reviewed in (1–3)). The most common pathogen in adults with CF is Pseudomonas aeruginosa, which affects 80% of the CF population (4). Nebulized sodium nitrite may represent a new therapeutic approach for the treatment of P. aeruginosa infection. Sodium nitrite has in vitro antimicrobial activity against P. aeruginosa and other airway pathogens (5–7). Nebulized sodium nitrite has an excellent safety profile from ongoing studies in pulmonary hypertension. In CF, there is the potential for bronchospasm in subjects with CF-related airway hyperactivity, thus a safety study such as the one proposed is warranted.

Study Objectives:	The objective of this research study is to determine whether nebulized sodium nitrite is safe in adults with cystic fibrosis.
Study Hypothesis:	The hypothesis of this study is: Nebulized sodium nitrite will be well tolerated by adults with CF.
Study Aims:	
Specific Aim:
 
1. Determine the safety of nebulized sodium nitrite administered in two doses to patients with CF.2. Explore the effects of inhaled sodium nitrite on measures of lung function, exhaled airway nitric oxide, and bacterial burden as measured by quantitative sputum cultures.
Study type	This is an experimental study of a new inhalation solution for cystic fibrosis. The initial study is a Phase I/II open-label design enrolling a total of 35 subjects that meet all the eligibility criteria.
Planned Sample Size:	35 Subjects
Duration of Treatment:	56 days
Inclusion Criteria:	
1. Subjects 18 years or older with CF as documented by clinical features of CF, and documentation of a positive sweat test or two disease causing mutations in the CF gene, will be eligible.

Exclusion Criteria:	
1. Inability to provide consent2. Use of supplemental oxygen or non-invasive ventilatory support3. FEV₁ < 40%4. Awaiting lung transplantation5. Pregnancy or unwilling to comply with birth control during the intervention period6. History of glucose-6-phosphate dehydrogenase (G6PD) deficiency or any contraindication to receiving methylene blue7. Hospitalization within the past 4 weeks prior to enrollment8. Subject requires additional antibiotics or steroids within the past 4 weeks prior to enrollment9. Change in maintenance CF therapies in the past 4 weeks prior to enrollment10. Baseline systemic hypotension (systolic BP < 90 mm Hg)11. History of orthostatic hypotension or syncope12. Chronic kidney disease (creatinine > 2.5 or requiring dialysis)13. Severe anemia (Hgb <9 gm/dL in the last six months)14. History of portal hypertension or chronic liver disease, including hepatitis B and/or hepatitis C (with evidence of recent infection and/or active virus replication), defined as moderate to severe hepatic impairment (Child-Pugh Class B-C)15. History of abusing alcohol or illicit drugs within 28 days prior to study16. Severe pulmonary hypertension (mean PA pressure > 25)17. Use of sildenafil or other pulmonary vasodilator18. History of any organ transplantation19. Participation in another interventional trial in the previous 28 days
Study Endpoints:	
Primary endpoint:
 
The primary safety and efficacy endpoint is FEV₁. A sustained decrease in FEV₁ of >15% will be considered intolerable.
 
Secondary endpoints include exhaled NO (FE_{NO}), sputum nitrite concentration, quantitative bacterial cultures, percutaneous methemoglobin levels, blood pressure, and subject symptoms as measured by the CF Questionnaire-R.

1. OBJECTIVE, SPECIFIC AIMS, BACKGROUND, AND SIGNIFICANCE

1.1 OBJECTIVE

The objective of this research study is to determine the safety of nebulized sodium nitrite administered in a dose escalation manner in adults with cystic.

1.2 SPECIFIC AIMS

Hypotheses:

(1) Nebulized sodium nitrite will be well tolerated by adults with CF.

To determine the therapeutic potential of sodium nitrite for CF, we propose two specific aims:

Specific Aims:

Aim 1: Determine the safety of nebulized sodium nitrite administered in two doses to patients with CF.

Aim 2: Explore the effects of nebulized sodium nitrite on measures of lung function, exhaled airway nitric oxide, and bacterial burden.

1.3 BACKGROUND

1.3.1 Cystic Fibrosis and Chronic Airway Infections

Cystic fibrosis (CF) is the most common severely life-shortening genetic disease of Caucasians. Tenacious mucus plugs the airways and becomes chronically infected (reviewed in 1-3). Ongoing infections lead to bronchiectasis and ultimately death from chronic respiratory failure. The most common pathogen in adults with CF is *Pseudomonas aeruginosa*, which affects 80% of the CF population (4). Current treatment focuses on monthly cycled of inhaled antibiotics such as tobramycin and aztreonam(8). However, over decades bacteria become resistant to all existing antibiotics. There is an additional 10% of the CF population infected with organisms such as *B. cepacia complex* for which there are no existing inhaled antimicrobial therapies(4). Despite the magnitude of disease caused by *P. aeruginosa* and other airway pathogens, we do not have adequate antibiotic therapies to either keep colonization in check or eradicate the organism. This will continue to be an unmet therapeutic need as the CF population ages and is exposed to additional decades of antibiotics.

Nebulized sodium nitrite may represent a new therapeutic approach for the treatment of *P. aeruginosa* infection. Previous work by [name] demonstrated that nitrite has bactericidal activity against *P. aeruginosa* growing in liquid culture, with mucoid strains and anaerobically growing bacteria being 2-5 fold more sensitive(5, 6). We have extended this work and shown that nitrite prevents biofilm growth by *P. aeruginosa* growing on the surface of primary human

airway epithelial cells(7). The effect ceiling is 50 mM, which is near the estimated airway concentration of nitrite after nebulization. In addition to anti-Pseudomonal activity, nitrite has antimicrobial activity against other CF pathogens including *Staphylococcus aureus*, *Burkholderia* spp and *Achromobacter* spp(5, 7, 9). The broad activity of nitrite is a unique strength of the agent as an antimicrobial agent.

Within the lung, the chemistries of nitrite and nitric oxide (NO) are closely related. Nitrite is reduced to NO both enzymatically and nonenzymatically. NO is formed when nitrite reacts with metal containing proteins such as hemoglobin and cytochrome c oxidase (mitochondrial complex 4)(10). These reactions are influenced by both pH and oxygen tension, and occur more rapidly under acidic conditions with a low oxygen tension, such as those found in the CF lung (6). NO has a biologic half-life of milliseconds and is the principle regulator of pulmonary vascular tone. With a half life of 51 minutes when delivered IV (and potentially longer when inhaled), nitrite can be viewed as a long acting source of NO(11, 12). In addition to its role as a vasodilator, nitrite plays a role in innate immunity. In the epithelium NO is produced by inducible nitric oxide synthetase (iNOS) from L-Arginine. In the healthy lung, both the airway epithelium and immune cells produce NO. However, in CF the airway epithelium expresses much less iNOS leading to decreased exhaled nitric oxide (13). Low exhaled nitric oxide levels are correlated with worse lung function as well as *P. aeruginosa* colonization in CF (14). Because NO has strong antimicrobial effects, low NO levels in the airway may contribute to the susceptibility to bacterial colonization in CF. Nitrite has the theoretical added benefit of restoring normal airway NO levels in patients, such as those with CF, who have an endogenous NO production defect. The antimicrobial activity of nitrite derives from its ability to inhibit bacterial respiration(7, 15). The precise molecular targets are an area of active investigation, but nitrite can inactivate heme-containing proteins (such as cytochrome c oxidases), disrupt iron-sulfur containing proteins (such as NADH dehydrogenase and succinate dehydrogenase), and S-nitrosate redox active cysteine residues impairing protein function (16). Nitrite was initially proposed as an inhaled antimicrobial agent in 2006 by [name] group, however compound to perform clinical trials was not available until recently and preclinical safety data was not previously available.

1.3.2 Investigational Drug

The study material (nebulized sodium nitrite) is sodium nitrite in a sterile aqueous solution. It is FDA-approved for intravenous use. We will be nebulizing the solution in the current study. The solution is packaged at 30 mg/mL. Thus 1.5 ml will be nebulized for a 45 mg dose and 3ml will be nebulized for a 90mg dose.

1.3.3 Rationale for Dose of Nitrite

The doses of nitrite proposed (45 mg and 90mg) were chosen based on existing human safety data and *in-vitro* antimicrobial data. In healthy volunteers, the maximum tolerated dose of nitrite was 90 mg(12). In the initial study CS01, 2/6 subjects experienced symptomatic hypotension and tachycardia at a dose of 176 mg. This effect occurred immediately after nebulization, and thus for CS01 the MTD was 125mg. In study CS04, 2/3 subjects had transient, but symptomatic, orthostasis with 120 mg, thus the MTD was lowered to 90mg. No other dose limiting toxicity

was seen at 90 mg. This study included dosing subjects with mild hypoxia (such as might be seen in patients with end stage lung disease) and no interaction was seen between hypoxia and nebulized nitrite. Methemoglobin did not exceed 3% in these studies. Subsequently, in a study of 36 participants with pulmonary hypertension, no increase in methemoglobin was seen with 90 mg doses (17). Another study on heart failure with preserved ejection fraction found no increase in methemoglobin as compared to control (18). Methemoglobin levels above 30% of total hemoglobin can cause shortness of breath due to the reduced oxygen carrying capacity, and levels above 50% can lead to seizures and death(19). In these studies, nebulized sodium nitrite was dosed up to every 8 hours for 6 days. Thus at doses up to 90mg, nebulized sodium nitrite appears safe in healthy subjects for dosing. Additional, unpublished safety data is available from Phase 2b clinical trials that were terminated with the sale of the sponsor company. More than 30 subjects with pulmonary arterial hypertension have been treated for as long as 12 months with no treatment related serious adverse events. In the recently completed studies of inhaled nitrite for pulmonary hypertension, doses of 46 or 80 mg four times daily were reportedly well tolerated for up to 16 weeks. Since initial submission of this protocol, additional safety data in 36 patients with pulmonary hypertension and heart failure with preserved ejection fraction have been published. In these studies, one subject was withdrawn due to asymptomatic hypotension, and the only side effect reported was occasional self-limited cough (17, 18). Regarding the doses where nitrite may have antimicrobial activity, we estimate that with a dose of 46 mg in a high efficiency nebulizer no less than 50% of the dose will reach the lower airways. Assuming a volume of distribution in the airway surface liquid of at most 7 mL, we estimated that the initial sodium nitrite concentration in the airway after nebulization of a 46 mg dose will be 47 mM, and with 80 mg, 82 mM. In the CF airway, assuming surface liquid depletion, these are likely conservative estimates and the immediate post-deposition concentration may be higher. Importantly, these estimated concentrations are above the concentrations that we found reduce biofilm growth of *P. aeruginosa* (1 log reduction at 15 mM)(7). Based on these considerations, in this safety and proof of concept study, we will target dosing above the concentrations necessary for an anti-microbial effect and two fold below the maximal tolerated dose in normal volunteers. Dosing will be 45 mg (controlled by the nebulizer) for the first week to provide multiple day safety data prior to observed escalation to the target 90 mg dose for the remaining three weeks of the study

1.4 SIGNIFICANCE

Chronic airway infections with multi-drug resistant Gram-negative organisms are common in patients with structural lung diseases, particularly CF but also including those with non-CF bronchiectasis, COPD, following lung transplant, and those with chronic airway hardware such as tracheostomies. The current FDA approved inhaled antibiotics are limited to tobramycin and aztreonam, to which many organisms are resistant. We hypothesize that inhaled nitrite provides an innovative therapeutic approach for patients with chronic airway infections because:

1. Nitrite has broad antimicrobial activity against all organisms tested, including respiratory isolates of *Burkholderia cepacia* complex, *Staphylococcus aureus*,

Achromobacter complex, and *Klebsiella pneumoniae*(5, 9). This study will provide proof-of-concept efficacy data that nitrite inhibits bacterial growth.

2. The antimicrobial activity of nitrite increases under anaerobic and acidotic conditions such as those found in the CF airway. Both low pH and oxygen tension decrease the activity of many antibiotics.
3. This study will provide evidence that nebulize nitrite can reconstitute the NO deficiency found in CF.
4. The results obtained in this study will lay the groundwork for future large scale clinical trials needed to determine the efficacy of inhaled nitrite as an antibiotic in patients with cystic fibrosis and other patient populations with chronic airway infections.

2. STUDY DESIGN AND METHODS

2.1 CLASSIFICATION AND METHODOLOGICAL DESIGN

This is a single-center, open label phase I/II study to determine the safety of inhaled nitrite in adults with cystic fibrosis.

2.2 STUDY DESIGN AND METHODS

2.2.1 *Study Design*

A total of 35 subjects with a confirmed diagnosis of cystic fibrosis meeting all the eligibility criteria will receive the investigative drug, nebulized sodium nitrite. The starting dose of nebulized sodium nitrite is 45 mg for the first week to provide multiple dose safety data and subject tolerability prior to the observed escalation target dose of 90 mg for the remaining three weeks of the study.

Screening (day -28 to -2): Potential subjects will be recruited from the CF Center at Children's Hospital of Pittsburgh and/or the UPMC Comprehensive Lung Center (CLC). In these locations, individuals with CF are followed on a routine basis and are well known to the study investigators. Initial screening evaluations including urine pregnancy test (only on females of childbearing potential), physical examination, medical history, and clinical laboratory assessments will be conducted to determine study eligibilities during a routine clinic visit. If a patient has had the required screening laboratory assessments within the past 6 months, results of those tests will be used for screening purposes and only repeated if clinically significant abnormalities were identified. In addition, vital signs (pulse, non-invasive blood pressure measurement, temperature, respiratory rate and oxygen saturation) will be performed. Subjects who meet the inclusion criteria and none of the exclusion criteria will be entered into the study and baseline spirometry will be obtained with the study spirometer. If the participant is on inhaled antibiotics, Visit 1 will be scheduled 2-7 days after the participant initiates the next scheduled inhaled antibiotic. Subjects are to remain on the same inhaled antibiotic through the end of Visit 5. Remaining on the same inhaled antibiotic for more than one month is quite common in CF clinical care.

Experimental Procedures (visit 1/day 0 (+/- 1day)): This visit will take approximately 5 hours. Subjects will arrive and complete the CFQ-R CF Questionnaire. Vital signs will be recorded and a physical examination performed, subjects will provide a sputum sample if able, and complete an oral wash specimen. The fractional excretion of nitric oxide (FENO) will be measured using a NIOX device, and baseline spirometry will be obtained. If subjects are unable to spontaneously expectorate sputum, then sputum induction will be done, followed by at least a 30 minute observation period because sputum induction is associated with temporary bronchoconstriction which might confound further measurements. The observation period will be omitted in subjects that spontaneously expectorated sputum. Next, an electronic nebulizer will be used to deliver 45 mg of nebulized sodium nitrite. Subjects will be monitored closely for the next two hours, including percutaneous measurements of oxygen saturation and methemoglobin levels, recorded at minutes 15, 30, 60 and 120, and noninvasive systemic blood pressure measurements every 15 minutes. Spirometry will be repeated at 30 and 120 minutes following nebulized sodium nitrite administration. If percutaneous methemoglobin measurements exceed 5%, they will be confirmed by venous blood measurement. If nebulized sodium nitrite is tolerated, then the subject will be dispensed an 8 day supply of 45 mg nebulized sodium nitrite dosed two times daily and discharged from the CTRC, CHP or the Emphysema Research Center in Montefiore. If the 45mg dose of nebulized sodium nitrite is not tolerated, the subject will be observed until stable and then discharged from the CTRC, CHP or the Emphysema Research Center in Montefiore.

Experimental Procedure (visit 2/day 7 (+/- 1day)): This visit will take approximately 5-7 hours. Subjects will arrive and complete the CFQ-R CF Questionnaire. FENO will be measured as above. If the subject had no serious adverse events for the first seven days of the 45 mg dose of nebulized sodium nitrite, and has stable systemic blood pressure and FEV₁ on presentation to the Day 7 visit, an electronic nebulizer will be used to deliver 90 mg of nebulized sodium nitrite. Subjects will be monitored closely for the next two hours, including percutaneous measurements of oxygen saturation and methemoglobin levels, recorded at minutes 15, 30, 60 and 120, and noninvasive systemic blood pressure measurements every 15 minutes. If percutaneous methemoglobin measurements exceed 5%, they will be confirmed by venous blood measurement. Spirometry will be repeated at 30 and 120 minutes following nebulized sodium nitrite administration. If nebulized sodium nitrite is tolerated, then the subject will be dispensed an 8 day supply of 90 mg nebulized sodium nitrite dosed two times daily and discharged from the CTRC, CHP or the Emphysema Research Center in Montefiore. If the 90 mg dose of nebulized sodium nitrite was not tolerated, the subject will be observed. If FEV₁ returns to baseline in 4 hours and subject's SaO₂ is not greater than 5% drop from baseline and systolic BP is not greater than 40 mm Hg drop from pre-dose baseline, the subject will be re-challenged at this visit with a 45 mg dose of nebulized sodium nitrite and the observation protocol of blood pressure measurements, spirometry and percutaneous oxygen saturation measurement will be repeated.

Experimental Procedures (visit 3/day 14(+/- 1day)): This is a safety and tolerability visit and will take approximately 1 hour. Subjects will complete the CFQ-R and spirometry. An oral wash will be collected, and then a sputum sample will be collected. If the subject cannot spontaneously expectorate, then sputum induction will be done. The subject will then be discharged with a 15 day supply of nebulized sodium nitrite.

Experimental Procedures (visit 4/day 28(+/- 1day)): This visit will take approximately 1.5 hours. Subjects will complete the CFQ-R and spirometry. Expectorated or induced sputum will be collected, an oral wash will be collected, and FE_{NO} measured as above. Sputum will be used to measure nitrite concentration and quantitative bacterial load.

Experimental Procedure (visit 5/day 42(+/- 5day)): This visit will take approximately 1 hour. Subjects will complete the CFQ-R and have spirometry, an oral wash will be collected, expectorated or induced sputum will be collected, physical exam, vital signs (pulse, non-invasive blood pressure measurement, temperature, respiratory rate and oxygen saturation) and interval history assessment will be performed.

Subjects will be monitored carefully for adverse events, laboratory test abnormalities, and changes in vital signs. Adverse experiences will be evaluated according to criteria outlined in the NCI Common Terminology Criteria for Adverse Events (CTCAE), version 4.0

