2.3 STUDY TREATMENT

The study treatment will be delivery of nebulized sodium nitrite by nebulization at the dose of 45 or 90 mg.

Table 1 Dose Limiting Toxicity Criteria

Sign or Symptom	Moderate	Severe ¹
Bronchospasm/ wheezing	Symptomatic but not requiring therapy	Symptomatic and requiring therapy
Decrease in FEV_1	>15%	>25%
SBP ²	Systolic \geq 20 mm Hg drop from pre-dose baseline AND symptomatic, or SBP <80 mm Hg AND symptomatic	Systolic > 30 mm Hg drop from pre- dose baseline AND symptomatic or requiring fluid replacement or other therapy
Dyspnea	Causes more discomfort (than a mild, easily tolerated AE) and interrupts the subject's usual daily activities	Incapacitating and causes considerable interference with the subject's usual daily activities
Cough	Causes more discomfort (than a mild, easily tolerated AE) and interrupts the subject's usual daily activities	Incapacitating and causes considerable interference with the subject's usual daily activities
Hypoxia ³	$SaO_2 > 5\%$ drop from baseline AND symptomatic	$SaO_2 \geq 10\%$ drop from baseline or $SaO_2 < 88\%$ AND symptomatic

Percutaneous methemoglobin ^{4,5}	>5% and <7%	≥7%
Other drug-related signs or symptoms ⁶	Causes more discomfort (than a mild, easily tolerated AE) and interrupts the subject's usual daily activities OR CTCAE v.4 ⁶ Grade 2 toxicity	Incapacitating and causes considerable interference with the subject's usual daily activities OR CTCAE v.4 ⁶ Grade 3 or 4 toxicity

AE = adverse event; CTCAE = Common Toxicity Criteria for Adverse Events; DLT = dose limiting toxicity; SBP = systolic blood pressure; SaO₂ = oxygen saturation (hemoglobin)

1. Severe DLT seen in any subject which is deemed to be study drug-related will preclude further dosing with nebulized sodium nitrite for that subject.
2. Moderate or Severe SBP without symptoms will be continuously monitored with BP measurements every 5 minutes. Symptomatic refers to dizziness or fainting. Discontinuation of further dosing or dose escalation will be based upon follow up blood pressure measurements, subject symptoms and physician-investigator discretion (see Stopping Rules).
3. Moderate or Severe SaO₂ without symptoms will be continuously monitored and recorded every 5 minutes until return of saturation > 92%.

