2.6 STOPPING RULES

Two distinct scenarios in which subjects must be removed from the study are anticipated.

First, the subject experiences a CF respiratory exacerbation marked by a persistent drop in FEV1 >15% that is not temporally associated with nebulized sodium nitrite administration. The drop in FEV1 would be seen on the first set of spirometry at a visit, prior to dosing of nebulized sodium nitrite for that day. In this case, subjects will be removed from the study and referred to their pulmonologist for treatment of the CF respiratory exacerbation.

Drop in FEV1 >15% on the first set of spirometry, prior to drug administration, on any study visit when compared with baseline spirometry collected at screening.

In the second scenario, nebulized sodium nitrite is associated with a dose-dependent intolerance that will be seen at the dose escalation visit 2, or after receiving the first dose of drug on visit 1. Specific intolerances of concern are acute bronchospasm, hypotension or methemoglobinemia. In this case, if any one of the below occurs at the 45 mg dose, subject will be removed from the study; if any occur at the 90 mg dose, the subject will return to the previously tolerated dose of 45 mg.

Specific criteria for dose-dependent intolerance are:

Decrease in FEV1 by >15% between measurements on an individual study visit.

A decrease in systolic BP > 40 mmHg drop from pre-dose baseline or to <80mmHg and symptomatic.

SaO₂ drop below 88% and symptomatic or SaO₂ desaturation > 5% from baseline and symptomatic

A single occurrence of venous methemoglobin level >5%

Any serious adverse event thought to be possibly related to the study treatment

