2.14.2 WITHDRAWL CRITERIA

Study treatment will be discontinued in individual subjects during the day 0 inhalation if any of the following occurs regardless of symptoms:

- **Decrease in FEV₁ by >15%** between measurements on an individual study visit.
- A decrease in systolic BP > 40 mm Hg drop from pre-dose baseline or to <80mmHg and symptomatic;
- SaO₂ drop below 88% and symptomatic or SaO₂ desaturation > 5% from baseline and symptomatic
- A single occurrence of venous methemoglobin level >5%;
- Any serious adverse event thought to be possibly related to the study treatment

Any serious adverse event thought to be possibly related to the study treatment

If a study subject tolerates the 45 mg dose but develops hypotension, sustained > 15% decrease in FEV₁ (as measured at time points (30min and 120 min), or oxygen desaturation with the 90 mg dose on day 7, the subject will be observed. If after 4 hours of observation the subject's FEV₁ returns to baseline, the subject's SaO₂ is not greater than 5% drop from baseline, and the subject's systolic BP is not greater than 40 mm Hg drop from pre-dose baseline, the subject will be re-challenged with the 45mg dose; if the lower dose is tolerated, the subject will remain in the study at the lower dose.

Subjects will be withdrawn if at any time the investigator feels that it is not in the subject's best interest to continue.

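### The day-7 test for a same-day 45 mg re-challenge looks only at the size of the systolic fall and leaves out the symptomatic below-80 limb that defines intolerance at 90 mg

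*Combined protocol and SAP*

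**What the plan says.** Four places in the protocol bear on a blood-pressure reaction to the first 90 mg dose at visit 2.

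- **Section 2.6 (copied in 5.5.2)** defines intolerance as "A decrease in systolic BP > 40 mmHg drop from pre-dose baseline or to <80mmHg and symptomatic". Its consequence is that "if any occur at the 90 mg dose, the subject will return to the previously tolerated dose of 45 mg". It states no recovery condition and no exception for severe events.
- **Section 2.2.1, visit 2**, sets the re-challenge test: FEV1 back to baseline, SaO2 down by no more than 5%, and "systolic BP is not greater than 40 mm Hg drop from pre-dose baseline, the subject will be re-challenged at this visit".
- **Section 2.14.2** repeats the test, after four hours of observation: "systolic BP is not greater than 40 mm Hg drop from pre-dose baseline, the subject will be re-challenged with the 45mg dose". It adds that "if the lower dose is tolerated, the subject will remain in the study at the lower dose".
- **Section 2.3, Table 1**, grades a systolic event as moderate at a fall of 20 mm Hg or more "drop from pre-dose baseline AND symptomatic, or SBP <80 mm Hg AND symptomatic". It is severe at "Systolic > 30 mm Hg drop from pre- dose baseline AND symptomatic", or if fluid or other therapy is needed. Footnote 1 says "Severe DLT seen in any subject which is deemed to be study drug-related will preclude further dosing with nebulized sodium nitrite", and section 2.5 repeats that consequence. Footnote 2 takes symptomatic to mean dizziness or fainting. It leaves decisions on further dosing to follow-up pressures, symptoms and physician discretion.

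**The concern.** The test that lets a subject back onto drug is looser than the rule that took the subject off. FEV1 must return to baseline. Systolic pressure need not recover at all if intolerance was declared on the symptomatic below-80 limb, because the re-challenge test keeps only the 40 mm Hg fall. Both re-challenge sentences are worded as instructions, not options.

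The same sentences also cross Table 1. A symptomatic fall of 31 to 40 mm Hg is a severe dose-limiting toxicity (DLT), which ends dosing if it is drug-related, yet it satisfies the re-challenge test. Staff cannot follow both rules.

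Hypotension is one of the two toxicities that section 2.5 expects from this drug, and symptomatic orthostasis at 120 mg is why section 1.3.3 puts the maximum tolerated dose at 90 mg. The re-challenge is also the last decision based on measured blood pressure during treatment. Section 2.10 and the schedule in 2.11 show no blood pressure at day 14 or 28, and the next is at day 42.

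**Working it through.** The plan gives no computed figure on this point, so the check sets the rules against each other.

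**Notation.** Let p be systolic pressure before the 90 mg dose, n the pressure when the test is applied, and d = p − n, in whole mm Hg, with symptoms present. Entry excludes p below 90 (section 3.3). I assume the day-7 value is also at least 90, since the plan asks only that it be stable.

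**Rules.**
- Intolerant (2.6): d > 40 or n < 80.
- Passes the re-challenge systolic limb (2.2.1, 2.14.2): d ≤ 40, that is n ≥ p − 40.
- Severe (Table 1): d > 30, or therapy given.

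**Step 1: intolerant, yet passing with no recovery.** This needs p − 40 ≤ n ≤ 79, so p ≤ 119. It is possible for every p from 90 to 119. From p = 120 upward, d ≤ 40 already implies n ≥ 80.

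**Step 2: the part that footnote 1 does not reach.** Without therapy, the event is not severe when d ≤ 30. Then p − 30 ≤ n ≤ 79, so p ≤ 109.

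| p | n, intolerant and passing, not severe | n, intolerant and passing, severe |
|---|---|---|
| 90 | 60–79 | 50–59 |
| 100 | 70–79 | 60–69 |
| 109 | 79 | 69–78 |
| 110 | none | 70–79 |
| 119 | none | 79 |
| 120 | none | none |

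Example: p = 100, n = 78, dizzy, untreated. Here d = 22. The subject is intolerant under 2.6 (78 < 80) and moderate under Table 1 (22 is at least 20 and not above 30). The subject passes the re-challenge limb (22 ≤ 40).

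**Step 3: the conflict.** Take p = 115, n = 78, dizzy: d = 37. Table 1 grades this severe, so if it is drug-related, footnote 1 and section 2.5 end dosing. The re-challenge limb is passed (37 ≤ 40). The same clash arises for d = 31 to 40 with n ≥ 80, which needs p ≥ 111. Those falls are not 2.6 events. They enter the day-7 path only through the term hypotension in 2.14.2, which is not defined there.

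**Step 4: what follows the re-challenge.** Section 2.6 removes a subject who is symptomatic below 80 at 45 mg. An unrecovered subject of Step 2 therefore receives one observed dose of 45 mg and is then out. It is different for a drug-related severe DLT that has improved enough to pass. Footnote 1 gives 0 further doses. The re-challenge text gives the re-challenge and then home dosing from day 7 to day 28: about 21 × 2 = 42 doses, or 42 × 45 = 1,890 mg.

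**Step 5: how likely non-recovery is.** Section 1.3.1 gives an intravenous half-life of 51 minutes. Four hours is 240 / 51 = 4.7 half-lives, and 0.5^4.7 ≈ 0.04, so about 4% remains. The same sentence says that the half-life may be longer when inhaled.

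**Step 6: after the fix.** If passing also requires n ≥ 80 and no symptoms, no pair with p from 90 to 140 is both intolerant under 2.6 and able to pass unchanged.

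**The case against.** The strongest reply is that the other safeguards leave little room for harm.

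- The re-challenge is observed with repeated pressures, at a dose the subject has just taken for a week, and section 2.6 applies to it. This stands. A reader might infer that a subject still dizzy below 80 would be sent home on three weeks of drug; the documents do not support that.
- The lowest passing pressures, down to 50 mm Hg from a pre-dose 90, look alarming, but each is a 40 mm Hg fall. If symptomatic it is severe, and footnote 1 bars the dose when it is drug-related. If asymptomatic it is not a below-80 event under 2.6. This also stands, so those limits do not measure the gap.
- Section 2.5 calls for toxicity to be treated, and treated hypotension is severe, which triggers footnote 1. This narrows the gap to untreated subjects but does not close it.
- Most subjects should have recovered by four hours. Section 1.3.3 calls the 120 mg events transient and reports no other dose-limiting toxicity at 90 mg. This limits the number affected. It does not repair a test whose purpose is to catch those who have not recovered.
- Footnote 1 can be read as overriding the re-challenge path, and the investigator may withdraw anyone. That is a sensible reading, but neither re-challenge sentence refers to footnote 1 or to symptoms. Discretion that has to override a direct instruction is a weak safeguard.

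**Conclusion.** The re-challenge test is wrong as written, in two limited ways. First, for pre-dose pressures of 90 to 109 mm Hg, a subject still symptomatic below 80 with a fall of 30 or less passes the systolic limb without recovery. Unless therapy was given, no explicit rule bars the dose. A subject who was intolerant through a fall above 40 must recover at least to 40. Second, for drug-related symptomatic falls of 31 to 40 mm Hg, Table 1 footnote 1 and section 2.5 contradict the re-challenge order.

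The direct exposure of a subject unrecovered below 80 is one observed 45 mg dose. About three weeks of home dosing is at stake only where a severe DLT has improved enough to pass the re-challenge.

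The number affected is unknown and probably small. The documents give no rate of symptomatic pressures below 80 at 90 mg. Multiplying an assumed rate by 35 would count everyone with the event, not those unrecovered at four hours, so I give no count. The conclusion assumes a day-7 pre-dose pressure of at least 90 and rests on the text of the rules, not on a predicted frequency.

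**What to change.** In sections 2.2.1 and 2.14.2, replace the systolic condition with: *no dizziness or fainting, SBP at least 80 mm Hg, and SBP not more than 40 mm Hg below that day's pre-dose value*. In both places, and after the 90 mg sentence in section 2.6 and its copy in 5.5.2, add: *A drug-related severe DLT is not re-challenged (Table 1, footnote 1).* In 2.6 and 5.5.2, make the return to 45 mg conditional on passing the re-challenge.

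These are the protocol's own thresholds. A tighter limb, such as recovery to within 20 mm Hg of pre-dose, is not needed to close the gap. It would also withhold drug after asymptomatic falls that Table 1 does not count as toxicity unless therapy is required.

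The cost is one reworded condition in two sections and short additions in four. No new measurement is needed, since pressure and symptoms are already observed. A few subjects may stop drug at day 7 and give no later 45 mg data.
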